### 9.4.3 ANALYSIS OF THE SECONDARY ENDPOINT(S)

For degree of concordance between therapists' feeding therapy frequency recommendations we have categorical data (2 groups – using and not using the tool; 3 response categories – 1xweek, 2xweek, less than 1 time per week). This is a repeated measure (therapists answer once for case A and once for case B). Each case will be analyzed separately. Due to the categorical data and small sample, reporting will be descriptive. Chi square tests will also be run if determined to meet the required assumptions. For chi-square tests, p value and effect size will be reported.

For degree of concordance between therapists' intervention target choices, descriptive statistics will be used due to the multiple categories (categorical data), small counts, and small sample size. The percentage of therapists recommending a particular provider will be compared among therapists using and not using the tool. This will be analyzed separately for case A and for case B.

For decision support tool acceptability, appropriateness, and feasibility, we have ordinal data (Likert scale). Additionally, each score (acceptability, appropriateness, feasibility) has 4 Likert scale items that form the score for that subscale. This is a single endpoint. The mean across the 4 items will be calculated for each participant to achieve a mean acceptability, appropriateness, and feasibility score. Then, the mean and standard deviation will be calculated across participants to result in an overall mean rating for acceptability, appropriateness, and feasibility.

Across all analyses, missing data will be reported but not corrected for due to the small sample size. Participants who did not complete all survey items will not be included in analysis. Adjustment for multiple comparisons is considered unnecessary due to the small sample size and minimal use of inferential statistics.

---

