## 3 OBJECTIVES AND ENDPOINTS

OBJECTIVES	ENDPOINTS	JUSTIFICATION FOR ENDPOINTS
Primary		

OBJECTIVES	ENDPOINTS	JUSTIFICATION FOR ENDPOINTS
Degree of Concordance Between Therapists' Feeding Therapy Recommendations	After reading a feeding case study, early intervention professionals will answer the question "Would you recommend feeding therapy?" with two choices: yes or no. Difference in agreement between early intervention professionals using the decision support tool and those not will be calculated and compared for cases A and B.	To determine whether using the tool, which helps identify feeding problem symptoms, changes decisions therapists make around recommending therapy for a child.
Degree of Concordance Between Therapists' Referral Recommendations	After reading a feeding case study, early intervention professionals will answer the question "Would you refer this family to any other providers/specialists for evaluation/treatment?" with two answer choices: yes or no. Difference in agreement between early intervention professionals using the decision support tool and those not will be calculated and compared for cases A and B.	To determine whether using the tool, which helps identify feeding problem symptoms by discipline with the explicit purpose of facilitating referrals, changes decisions therapists make around recommending referral to a specialist.
Degree of Concordance Between Therapists' Specific Specialist Referral Recommendations	After reading the feeding case study, early intervention professionals will answer the question "What other professionals would you refer this child to? Check all that apply." with the following choices: nutritionist/dietician, gastroenterologist, otolaryngologist (ENT), aerodigestive clinic, pulmonologist, occupational therapist, speech language pathologist, psychologist/social worker, applied behavior analyst (ABA), or allergist. Difference in agreement between early intervention professionals using the decision support tool and those not will be calculated and compared for cases A and B.	To determine whether the tool, which lists feeding problem symptoms by specialist discipline, changes the specialists a therapist refers to.
Secondary		

OBJECTIVES	ENDPOINTS	JUSTIFICATION FOR ENDPOINTS

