Degree of Concordance Between Therapists' Feeding Therapy Frequency Recommendations	After reading the feeding case study, early intervention professionals who recommended feeding therapy will answer the question "With what frequency would you recommend therapy?" with three choices: 2 times per week or more, 1 time per week, less than one time per week. Difference in agreement between early intervention professionals using the decision support tool and those not will be calculated and compared for cases A and B.	To determine whether using the tool, which helps identify feeding problem symptoms, changes decisions therapists make around recommending a specific frequency of therapy for a child.
Degree of Concordance Between Therapists' Intervention Target Choices	After reading the feeding case study, early intervention professionals who recommended feeding therapy will answer the question "What therapy targets might you include for this child?" and may check all that apply from the following choices: oral motor skills, sensory, behavioral, medication, modification of food/liquid, modification of equipment (seating, utensils, etc.), modification of environment (location, distractions, routine, etc.), parent coaching, or other. Difference in agreement between early intervention professionals using the decision support tool and those not will be calculated and compared for cases A and B.	To determine whether using the tool, which helps identify feeding problem symptoms by area of concern, changes decisions therapists make around recommending a specific intervention target for a child.
Decision Support Tool Acceptability Score	The Acceptability of Intervention Measure (AIM) will be used to measure acceptability of the decision support tool. This tool includes four items, rated on a five-point Likert scale from completely disagree to completely agree, and will be quantified with a score of 0 for completely disagree, 1 for disagree, 2 for neither agree nor disagree, 3 for agree, and 4 for completely agree. The average score across the four items will be calculated, with higher	To determine if this intervention is acceptable to practicing therapists.

OBJECTIVES	ENDPOINTS	JUSTIFICATION FOR ENDPOINTS

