### 9 STATISTICAL CONSIDERATIONS

#### 9.1 STATISTICAL HYPOTHESES

- Primary Efficacy Endpoint(s):
  - Degree of concordance between therapists’ feeding therapy recommendations
    - Null Hypothesis: There is no difference in therapists’ feeding therapy recommendations when using v. not using the tool

- Alternative Hypothesis: There is a difference in therapists' feeding therapy recommendations when using v. not using the tool
- Non-inferiority comparison
- Time period: After reading the case study
- Degree of concordance between therapists' referral recommendations
  - Null Hypothesis: There is no difference in therapists' referral recommendations when using v. not using the tool
  - Alternative Hypothesis: There is a difference in therapists' referral recommendations when using v. not using the tool
  - Non-inferiority comparison
  - Time period: After reading the case study
- Degree of concordance between therapists' specific specialist referral recommendations
  - Null Hypothesis: There is no difference in who the therapists recommend referral to when using v. not using the tool
  - Alternative Hypothesis: There is a difference in who the therapists recommend referral to when using v. not using the tool
  - Non-inferiority comparison
  - Time period: After reading the case study
- Secondary Efficacy Endpoint(s):
  - Degree of concordance between therapists' feeding therapy frequency recommendations
    - Null Hypothesis: There is no difference in therapists' feeding therapy frequency recommendations when using v. not using the tool
    - Alternative Hypothesis: There is a difference in therapists' feeding therapy frequency recommendations when using v. not using the tool
    - Non-inferiority comparison
    - Time period: After reading the case study
  - Degree of concordance between therapists' intervention target choices
    - Null Hypothesis: There is no difference in therapists' feeding therapy intervention target choices when using v. not using the tool
    - Alternative Hypothesis: There is a difference in therapists' feeding therapy intervention target choices when using v. not using the tool
    - Non-inferiority comparison
    - Time period: After reading the case study
  - Decision Support Tool Appropriateness
    - Null Hypothesis: The decision support tool is not appropriate.
    - Alternative Hypothesis: The decision support tool is appropriate.
    - Superiority
    - Time period: After using the tool

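### Section 9.4.3 names providers, not therapy targets, in the one comparison it gives for the intervention-target endpoint

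*Combined protocol and SAP*

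**What the plan says.** Section 3 defines this secondary endpoint by a question about therapy targets, put to therapists who recommended feeding therapy. They "may check all that apply from the following choices: oral motor skills, sensory, behavioral, medication, modification of food/liquid", and the list continues with equipment, environment, parent coaching and other. Section 9.1 states the null and alternative hypotheses on "feeding therapy intervention target choices when using v. not using the tool".

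Section 9.4.3 opens its paragraph on the endpoint correctly: for "intervention target choices, descriptive statistics will be used due to the multiple categories (categorical data), small counts, and small sample size". The next sentence gives the quantity to be compared: "The percentage of therapists recommending a particular provider will be compared among therapists using and not using the tool". The paragraph then closes with "This will be analyzed separately for case A and for case B".

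The middle sentence also appears, unchanged, in section 9.4.2 as the rule for the third primary endpoint. There it fits, because that endpoint rests on the item "What other professionals would you refer this child to? Check all that apply".

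**The concern.** An analysis rule should name the response that its endpoint measures. Here the paragraph announces one endpoint and then gives the measure of another. An analyst or programmer who follows the sentence as written would tabulate specialist referrals under the therapy-target heading, and the results would repeat what the third primary endpoint already reports.

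The error also hides a second gap. Because the sentence is about providers, the plan never says over whom a target percentage is taken. The target question is shown only after a yes to feeding therapy, and the tool is itself hypothesised to change that answer (sections 4.1 and 9.1). If the choice is left open, it may be made after the data have been seen.

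**Working it through.** The plan states no figure to reproduce. The check sets the passages side by side, counts what each reading delivers, and then illustrates the denominator.

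**1. The two endpoints side by side**

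| | Third primary endpoint | Intervention-target endpoint |
|---|---|---|
| Survey item | Which professionals the child would be referred to | Which therapy targets might be included |
| Shown after | Yes to referral (8.1) | Yes to feeding therapy (3 and 8.1) |
| Options | 10 in section 3; 12 in section 8.1, which adds the multidisciplinary feeding team and other | 9 in sections 3 and 8.1, counting other |
| Hypothesis in 9.1 | Whom therapists refer to | Which targets they choose |
| Quantity compared | Percentage recommending a provider (9.4.2) | Percentage recommending a provider (9.4.3) |

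The first four rows differ and the last is identical. No named option is on both lists. The only shared label is the free-text category, other, in section 8.1. Provider percentages therefore cannot give the target result.

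**2. Other text that might supply the rule**

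Section 9.4.1 says that descriptive statistics will be counts and percentages, but it names no response, denominator or contrast. No other sentence in section 9 says what is to be compared for therapy targets.

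**3. What each reading delivers**

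- With targets: 9 options x 2 cases = 18 pairs of percentages, tool against no tool, so 18 x 2 = 36 percentages.
- As written: 10 x 2 = 20 pairs, or 12 x 2 = 24 pairs with the section 8.1 list. These are provider percentages, already assigned to the third primary endpoint.

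**4. The denominator**

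Under sections 6.3 and 9.2, each sequence group has 14 SLPs + 14 OTs = 28 therapists. Within a case, one group answers without the tool and the other with it, so there are 28 per condition if enrolment goes as planned. The number who recommend therapy is not known in advance. As an assumed illustration, let 14 therapists in each condition tick the sensory target, and let 28 of 28 recommend therapy with the tool and 20 of 28 without it.

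- All completers: 14/28 = 50% with the tool, 14/28 = 50% without. Difference 0 points.
- Only those who recommended therapy: 14/28 = 50% with, 14/20 = 70% without. Difference 20 points.

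The same answers show no difference or a 20-point difference, depending only on the denominator. If the proportion recommending therapy is the same in both conditions, equal counts give equal percentages under either denominator and the gap disappears.

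**The case against.** The strongest reply is that this is a copying slip that no careful analyst would act on. The paragraph's first sentence assigns descriptive statistics to target choices, its last sentence adds the split by case, section 9.4.1 promises counts and percentages, and sections 3 and 9.1 define the endpoint and its hypothesis correctly. Together these point to target percentages by tool use and case. That stands, and it limits the seriousness of the point.

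A reader might infer that the plan never analyses therapy targets, or that their hypothesis is left with no analysis. The documents do not support this. The intent to describe targets is stated, and nothing suggests that the investigators mean to omit them. The lack of a formal test is not caused by the wrong word either: the plan chose description only for this endpoint, as it did for the third primary endpoint, where provider is the right word.

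It is also fair to say that the count of 36 percentages measures the extent of the mismatch. It shows no bias, loss of power or changed conclusion.

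The reply does not dispose of two things. The only explicit comparison rule for a prespecified endpoint names the wrong survey item. And the surrounding text, however generously read, does not settle the denominator.

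**Conclusion.** The point holds as a minor internal inconsistency. The sentence in 9.4.3 conflicts with its own paragraph, with section 3 and with section 9.1, and it should be corrected before analysis. Its reach is one descriptive secondary endpoint in a pilot whose sample size was set by funding and balance between groups.

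The textual part rests on the documents alone and needs no assumption. The denominator part depends on how far the proportion recommending therapy differs between conditions. The documents give no figure for this, so the 20-point illustration shows what is possible and does not predict a result.

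**What to change.** In section 9.4.3, replace the provider sentence with wording such as:

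> For each of the nine therapy-target options, we will report the number and percentage of therapists who select it, with and without the tool, and compare the two.

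Keep the sentence that follows, which separates case A from case B.

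Add a sentence on the denominator. One workable choice is all completers in that condition and case, counting therapists who were not asked the question as not selecting the target, with the number who recommended feeding therapy shown beside it. Readers can then derive the percentage among those asked.

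Confidence intervals for the differences are optional. The plan has none for any endpoint, and they are not needed to correct the error.

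The cost is two sentences in one section. Both survey items are already in section 8.1, so no new data are needed, and neither the randomisation nor the sample size is affected.

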#### 9.4.4 SAFETY ANALYSES

Survey responses will be monitored for any concerns responses and these will be reported.

---

#### 9.4.5 BASELINE DESCRIPTIVE STATISTICS

Intervention groups will be compared on the basis of years of experience (in feeding, early intervention, and overall clinical practice), and years since graduation with their clinical degree. Due to the small sample size, inferential statistics will be trialed (i.e. Mann-Whitney U), but may not be used if assumptions are not met for their appropriate use.

---

#### 9.4.6 PLANNED INTERIM ANALYSES

N/A

---

#### 9.4.7 SUB-GROUP ANALYSES

The primary and secondary endpoints will not be analyzed based on age, sex, or race/ethnicity for this pilot study due to the small sample size.

---

#### 9.4.8 TABULATION OF INDIVIDUAL PARTICIPANT DATA

Individual participant data will not be listed.

---

#### 9.4.9 EXPLORATORY ANALYSES

No exploratory analyses are planned.

## 10 SUPPORTING DOCUMENTATION AND OPERATIONAL CONSIDERATIONS

### 10.1 REGULATORY, ETHICAL, AND STUDY OVERSIGHT CONSIDERATIONS

#### 10.1.1 INFORMED CONSENT PROCESS

##### 10.1.1.1 CONSENT/ASSENT AND OTHER INFORMATIONAL DOCUMENTS PROVIDED TO PARTICIPANTS

Consent forms describing in detail the study intervention, study procedures, and risks are viewed by the participant and documentation of informed consent is required prior to starting intervention/administering study intervention. The following consent materials are submitted with this protocol Online Consent form.

##### 10.1.1.2 CONSENT PROCEDURES AND DOCUMENTATION

Informed consent is a process that is initiated prior to the individual's agreeing to participate in the study and continues throughout the individual's study participation. Consent forms will be Institutional Review Board (IRB)-approved and the participant will be asked to read and review the document. Interested participants will view an online version of the consent form via Qualtrics. They will be prompted to email the PI with any questions they have about the study. The professional will e-sign the consent form via Qualtrics to consent to participants.

The consent forms and processes will include information about the legal obligations of researchers that may, in rare instances, require a disclosure of confidential information. Professional participants will receive an emailed copy of their signed consent; original signed consent forms will be downloaded from Qualtrics and stored securely and separately from subject data on a secure UNC server.

Given the nature of the consent process, the research subjects will have time to read and think over the consent and whether they would like to participate, before signing. They will be offered the opportunity to ask the PI any questions before signing.

#### 10.1.2 STUDY DISCONTINUATION AND CLOSURE

This study may be temporarily suspended or prematurely terminated if there is sufficient reasonable cause. Written notification, documenting the reason for study suspension or termination, will be provided by the suspending or terminating party to study participants, investigator, funding agency, and regulatory authorities. If the study is prematurely terminated or suspended, the Principal Investigator (PI) will promptly inform study participants, the Institutional Review Board (IRB), and sponsor and will provide the reason(s) for the termination or suspension. Study participants will be contacted, as applicable, and be informed of changes to study visit schedule.

Circumstances that may warrant termination or suspension include, but are not limited to:

- Determination of unexpected, significant, or unacceptable risk to participants
- Insufficient compliance to protocol requirements
- Data that are not sufficiently complete and/or evaluable
- Determination that the primary endpoint has been met
- Determination of futility

Study may resume once concerns about safety, protocol compliance, and data quality are addressed, and satisfy the sponsor, and/or IRB.

#### 10.1.3 CONFIDENTIALITY AND PRIVACY

Participant confidentiality and privacy is strictly held in trust by the participating investigators, their staff, and the sponsor(s) and their interventions. Therefore, the study protocol, documentation, data, and all other information generated will be held in strict confidence. No information concerning the study or the data will be released to any unauthorized third party without prior written approval of the sponsor.

The study monitor, other authorized representatives of the sponsor, representatives of the Institutional Review Board (IRB), or regulatory agencies may inspect all documents and records required to be maintained by the investigator, including but not limited to, study records for the participants in this study.

The study participant's contact information will be securely stored on OneDrive for internal use during the study. At the end of the study, all records will continue to be kept in a secure location for as long a period as dictated by the reviewing IRB, Institutional policies, or sponsor requirements.

Study participant research data, which is for purposes of statistical analysis and scientific reporting, will be transmitted to and stored on UNC OneDrive. This will not include the participant's contact or identifying information. Rather, individual participants and their research data will be identified by a unique study identification number. The study data entry and study management systems used will be secured and password protected.

#### Certificate of Confidentiality

To further protect the privacy of study participants, a Certificate of Confidentiality will be issued by the National Institutes of Health (NIH). This certificate protects identifiable research information from forced disclosure. It allows the investigator and others who have access to research records to refuse to disclose identifying information on research participation in any civil, criminal, administrative, legislative, or other proceeding, whether at the federal, state, or local level. By protecting researchers and institutions from being compelled to disclose information that would identify research participants, Certificates of Confidentiality help achieve the research objectives and promote participation in studies by helping assure confidentiality and privacy to participants.

#### 10.1.4 FUTURE USE OF STORED SPECIMENS AND DATA

This study does not involve storage of specimens for future unspecified research.

#### 10.1.6 SAFETY OVERSIGHT

Because this study does not have any obvious safety concerns, provider responses to the survey will be monitored weekly for any concerning responses. Additionally, providers will be informed they should not yet use this tool in clinical practice.

---

#### 10.1.7 CLINICAL MONITORING

This study will be completed virtually and is low-risk (a survey). Clinical site monitoring will include monitoring of data entry. A random 20% of participant entries will be audited to ensure data is correctly transferred from the Qualtrics survey into data records for analysis.

---

#### 10.1.8 QUALITY ASSURANCE AND QUALITY CONTROL

The PI will manage all quality assurance and control. The survey will not be changed during the study unless approved by the IRB. Data will be downloaded and recorded by the PI and checked by a RA as necessary. QA and QC errors that are identified will be addressed by the PI.

---

